10.3 Deaths and Serious Adverse Events

A serious adverse event (SAE) is any event that is life threatening, results in death, causes or prolongs hospitalization, leads to a disability or birth defect, or requires an intervention to prevent a disability. SAEs will be listed and SAEs and treatment-related SAEs will be summarized in the manner mentioned in Section 10.2 if there are enough events to summarize. Deaths will be listed.

11 ANALYSIS OF OTHER OUTCOMES

No analyses of outcomes other than efficacy and safety outcomes are planned.

12 REPORTING CONVENTIONS

Unless required otherwise by a journal, the following rules are standard:

- Moment statistics including mean and standard deviation will be reported at 1 more significant digit than the precision of the data.
- Order statistics including median, min and max will be reported to the same level of precision as the original observations. If any values are calculated out to have more significant digits, then the value should be rounded so that it is the same level of precision as the original data.

- Following SAS rules, the median will be reported as the average of the two middle numbers if the dataset contains even numbers.
- Test statistics including t and z test statistics will be reported to two decimal places.
- P-value will be reported to 3 decimal places if > 0.001. If it is less than 0.001 then report '<0.001'. Report p-values as 0.05 rather than .05.
- No preliminary rounding should be performed, rounding should only occur after analysis. To round, consider digit to right of last significant digit: if < 5 round down, if >=5 round up.

13 CHANGES TO THE ANALYSIS PLANNED IN THE PROTOCOL

At the request of the DSMB, a sensitivity analysis will be conducted to assess the impact of including vs. excluding data from a clinical site at which potential data quality concerns were raised during conduct of the trial.

At the request of the writing team, additional endpoints describing the dryness status of participants based on the UDI and bladder diary responses will be added. For further details on how these diary indicators will be calculated, see Section 9.2.

Due to the relatively small number of participants who met failure (additional treatment) criteria, Kaplan Meier methods were used instead of the more complex survival modeling described in the protocol to compare MUS+BPTx vs. MUS alone.

Due to the relatively small number of women who met the improvement in voiding frequency definition (at least a 50% reduction in voiding frequency), the difference in improvement in voiding frequency between treatment groups could not be analyzed as described in Section 9.4 nor could the analysis that examined women who met both normalization and improvement in voiding frequency be performed.

15 LIST OF POTENTIAL DISPLAYS

Data displays may be added, deleted, rearranged or the structure may be modified after finalization of the SAP. Such changes require no amendment to the SAP as long as the change does not contradict the text of the SAP.

Tables
Participant Eligibility
Participant Disposition
Protocol Deviations
Demographic and Baseline Characteristics
Primary Efficacy Model Results
Secondary Efficacy Outcome Measures

Safety Summary Adverse Events
Figures
Consort diagram of participant disposition Initiation of Efficacy Kaplan Meier Curves (per outcome) Duration of Treatment Success Kaplan Meier Curves
Data Listings
Subject Eligibility Subject Disposition Protocol Deviations Adverse Events Serious Adverse Events

16 ATTACHMENTS

16.1 Defining Treatment Failures and Retreatment Rates

Treatment failure is defined as initiation of any additional treatment for either SUI or UUI/OAB symptoms. These will be determined through an analysis of the Additional Therapy Form (CRF #31) and Concomitant Medications Form (CRF #28).

- a. Additional Therapy Form – Any subject with a reported reason for visit of 2, 3, 4, 5, 10, 11, 12, 13, 14, 15, or 17 will be considered to have treatment failure at the time of the reported treatment. Similarly, each subject will be considered to have had retreatment.

2. Reason for Visit	6 = Pain	10 = Botox	16 = Other, specify
1 = UTI	7 = Infection	11 = Posterior tibial nerve stimulation symptoms	17 = sling removal
2 = Behavior Therapy	8 = Decrease efficacy (worsening incontinence)	12 = sling revision	18 = UUI/OAB
3 = PF Therapy	9 = Retention of urine or incomplete bladder emptying	13 = sling placement	19 = SUI symptoms
4 = Anticholinergic medication		14 = sacral neuromodulation	
5 = Pelvic PT		15 = Continence pessary	

- b. Concomitant Medications – Any subject with medications or therapies that are known treatments of OAB, UUI, or SUI (Detrol, Ditropan, Vesicare, Hyoscyamine, Oxybutynin) or for whom UUI/OAB, SUI Therapy, or Voiding Dysfunction indicators are marked will be considered to have treatment failure at the start date of the medication if it is after randomization. Similarly, each subject will be considered to have had retreatment.

Medication Name	Start Date (DD/MMM/YYYY)	Stop Date (DD/MMM/YYYY)	PRN	UUI/OAB Therapy	SUI Therapy	Voiding dysfunction	Continuing at End of Study
	___/___/___	___/___/___					

In general, any adverse events that could be considered treatment failures will be requested to be removed and re-entered on the additional therapies form if applicable.

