10.2 Adverse Events

Per the protocol, participants were asked to report any adverse events from initiation of treatment through 12 months follow-up. All adverse events were collected on an adverse event log and coded using MedDRA (V17.0).

Postoperative complications noted as adverse symptoms and events in the ESTEEM manual of procedures (MOP) (see table below) will be proactively reviewed and reported. ESTEEM complications are divided into “adverse symptoms” and “adverse events”. To help standardized the data collection process for complications, adverse symptoms and events will be captured as follows:

Adverse symptoms will be captured using either an active approach using validated questionnaires or an open-ended approach.

- a. Active capture for adverse symptoms: Specific patient-reported adverse symptoms will be identified by responses on validated questionnaires (denoted by * in table below). These 3 adverse symptoms include a patient report of new or worsening: 1) pelvic/vaginal pain, 2) sensation of incomplete bladder emptying (based on UDI responses) and 3) dyspareunia (based on PISQ-IR response). These are captured at 3, 6, and 12 months. To aid with retrospective collection of these AEs, the DCC will provide each site with a report listing longitudinal responses to the applicable UDI and PISQ-IR questions for participants who reported one of these symptoms at 3-12 months. The clinical site will report these adverse symptoms on the adverse events CRF per the usual process described in the MOP.

The clinical site will be responsible for reviewing the UDI and PISQ-IR responses for these 3 items and identifying any new or worsening symptoms. Once a new or worsening symptom is identified, the clinical site will track these adverse symptoms per the usual process in the MOP. Sites should review the UDI and PISQ-IR CRFs at the time the participant completes them so that any additional information needed to complete the adverse event CRF can also be collected at that time.

- b. Open-ended capture for adverse symptoms: 2 adverse symptoms will be captured using the open-ended approach because they are not captured in any of the validated questionnaires administered in ESTEEM. These include: 1) New/worsening partner dyspareunia and 2) New/worsening constipation. Using the open-ended approach, symptoms are captured if reported by the participant.

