Adverse events will be captured using the standard capture for AEs as described in the MOP and manually reviewed to determine which events meet the criteria for post-operative complication listed in the table below. This is an open-ended capture approach using chart review, physician report, or patient report corroborated by medical documentation.

Postoperative complications	
Adverse symptom	Definition

Network

Protocol ESTEEM Statistical Analysis Plan

New/worsening abdominal/genital pain at or beyond 3 month visit	UDI item N captured at 3, 6, 12 months and per patient report, chart review, physician report
New/worsening dyspareunia at or beyond 3 month visit	PISQ item C5 captured at 3, 6, 12 months and per patient report, chart review, physician report
New/worsening report of difficulty emptying bladder at or beyond 3 months	UDI item J captured at 3, 6, 12 months and per patient report, chart review, physician report
New/worsening partner dyspareunia at or beyond 3 month visit	Per patient report, chart review, physician report
New/worsening urge incontinence at or beyond 3 month visit	UDI item C captured at 3, 6, 12 months and per patient report, chart review, physician report
Adverse Event	
Postop need for catheter and/or ISC at or beyond 2 weeks	Captured by chart review, physician report, exam, or patient report corroborated by medical documentation
Vaginal mesh exposure	Captured by chart review, physician report, exam, or patient report corroborated by medical documentation
Vaginal mesh erosion into organ	Captured by chart review, physician report, exam or patient report corroborated by medical documentation
Other wound healing problems >6 weeks	Captured by chart review, physician report, exam or patient report corroborated by medical documentation
New/worsening vaginal infection	Captured by chart review, physician report, exam, or patient report corroborated by medical documentation
Urinary tract infection beyond 2 weeks	UTI based on clinical judgment or confirmation of culture proven, also includes empiric antibiotic treatment for symptoms thought to be due to UTI, or patient report corroborated by medical documentation. If a culture is sent that turns out to be negative, this would not be classified as a UTI. Captured by chart review, physician report, or patient report corroborated by medical documentation

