Other infection possibly related to intervention (sling and/or BPTx)	Infection diagnosed using clinical or radiologic indicators – not including vaginal infection, UTI Captured by chart review, physician report, or patient report corroborated by medical documentation
Non-study health care provider visit due to complication related to intervention (sling and/or BPTx)	Captured by chart review, physician report, or patient report corroborated by medical documentation

Emergency room visit due to complication related to intervention (sling and/or BPTx)	Captured by chart review, physician report, or patient report corroborated by medical documentation
Hospital readmission related to intervention (sling and/or BPTx)	Captured by chart review, physician report, or patient report corroborated by medical documentation
Reoperation related to surgery (any return to OR for issue related to intervention (e.g. recurrent SUI, UUI/OAB)	Captured by chart review, physician report, or patient report corroborated by medical documentation
An adverse event that is “unexpected” and “possibly, probably or definitely related”	Captured by chart review, physician report, or patient report corroborated by medical documentation

AEs will be listed and summarized by system organ class and preferred event term. Summaries will be of the number of events and number of individuals experiencing events by treatment group and will be created for all AEs, and AEs by severity. Any events starting outside of the reportable timeframe will be included in separate listings and will be excluded from summary tables. If a complete onset date is unknown and it cannot be confirmed that the event occurred during this time period, then the event will be considered a treatment-emergent AE.

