Adverse events will be individually reviewed to determine if they meet the conditions specified for each post-operative complication. The review will be conducted via keyword searches through reported event terms and comment for specific events (e.g. vaginal mesh exposure, ER visits, etc.) and by preferred term and system/organ class for more general complications (e.g. new/worsening vaginal infection, other infections, etc.). Worsening symptoms will be assessed by identifying worsening responses (compare to baseline) to the specific patient-questionnaire items identified at post-baseline collection times. Post-operative complications will be summarized by complication type. Summaries will be the number of individuals experiencing complications by treatment group.

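### SAP 16.1 may move adverse events that are also treatment failures off the adverse event log, while SAP 10.2 fills the reoperation and linked complication rows from recorded adverse events and does not read the Additional Therapy form.

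*SAP*

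**What the plan says.** **The removal rule.** SAP 16.1 defines treatment failure from two forms, the Additional Therapy form (CRF #31) and the Concomitant Medications form. The CRF #31 reasons that count as failure include sling revision (code 12), sling placement (13) and sling removal (17). The section ends with a data-handling rule: "any adverse events that could be considered treatment failures will be requested to be removed and re-entered on the additional therapies form if applicable". The sentence opens with the words in general, so it is a default and not an absolute instruction.

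**The safety displays.** SAP 10.2 states that "All adverse events were collected on an adverse event log and coded using MedDRA (V17.0". The postoperative complication table then divides into two kinds of row.

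- *Adverse events.* One row is "Reoperation related to surgery (any return to OR for issue related to intervention (e.g. recurrent SUI, UUI/OAB"). Others cover readmission and emergency visits related to the intervention. The method is: "Adverse events will be individually reviewed to determine if they meet the conditions specified for each post-operative complication". In practice, "The review will be conducted via keyword searches through reported event terms and comment for specific events".
- *Adverse symptoms.* Here "Worsening symptoms will be assessed by identifying worsening responses (compare to baseline) to the specific patient-questionnaire items". For new or worsening urge incontinence the source is "UDI item C captured at 3, 6, 12 months and per patient report, chart review, physician report".

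SAP 10.3 adds that "SAEs will be listed and SAEs and treatment-related SAEs will be summarized in the manner mentioned in Section 10.2" if there are enough of them.

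**What is counted from CRF #31.** SAP 9.2 takes two outcomes from it: retreatment by 12 months, with its type (together with the medication form), and sling revision for worsened OAB. SAP 9.5.5 reports both as rates. Protocol 5.1.c treats every sling revision as additional treatment, whatever its indication.

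**The concern.** One event can be a failure of treatment and a harm. A return to the operating room to revise a sling is the plainest case: SAP 16.1 counts it as failure, and the complication table in 10.2 asks for it by name. If the rule in 16.1 takes the record off the AE log, the review in 10.2 searches a log that no longer holds it, and no stated step brings it back from CRF #31.

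The reoperation row and the general AE summaries could then understate sling-related harm. Removal would also depend on retreatment, an outcome that the plan expects to differ between arms. On the planning assumption more records would leave the MUS-only arm, which would make MUS alone look safer than it was.

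**Working it through.** This is mainly a question of data sources, and no figure in the plan is contested. The first step traces each display to its source. The arithmetic after it only shows scale.

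**1. Tracing the displays**

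| Display | Stated source | Exposed to the 16.1 rule? |
|---|---|---|
| AE summaries (SAP 10.2) | AE log | Yes |
| Reoperation row (SAP 10.2) | Review of recorded AEs | Yes, for codes 12, 13 and 17 |
| Readmission and emergency visit rows (SAP 10.2) | Review of recorded AEs | Yes, when linked to such an event |
| Worsening-symptom rows assessed by questionnaire (SAP 10.2) | UDI and PISQ items against baseline | No |
| Sling revision for worsened OAB (SAP 9.2) | CRF #31 | No |
| Retreatment and its type (SAP 9.2) | CRF #31 and medication form | No |
| SAE listing and summary (SAP 10.3) | As in 10.2 | Not stated either way |

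The reoperation row is where the conflict is sharpest. Its own definition gives recurrent SUI and UUI/OAB as examples, and sling surgery for those reasons is a failure under 16.1. The same event is therefore required in the row and liable to removal from the row's source.

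**2. Denominator**

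SAP 6.3 starts from 200 per group and allows 15% dropout: 200 / (1 - 0.15) = 235.3, rounded up to 236 per arm. 2 x 236 = 472, which reproduces the stated total.

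**3. Sling revisions at stake**

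Protocol 5.1.c cites a revision rate of 0-1% from earlier sling trials, under the heading of urinary retention. Assumption: the same range holds here.

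- Per arm: 0 x 236 = 0, up to 0.01 x 236 = 2.36.
- Both arms: up to 2 x 2.36 = 4.72, about 5.

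The range is for revision only. The documents give no rate for sling placement or removal.

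**4. Women exposed to the rule, by arm**

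SAP 6 assumes additional treatment in 30% of the MUS-only arm and 20% of the MUS+BPTx arm.

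- MUS only: 0.30 x 236 = 70.8.
- MUS+BPTx: 0.20 x 236 = 47.2.
- Difference: 23.6.

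These are all women with any additional treatment. The share q who also had an AE entry that would be moved is not given. Over an assumed range:

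| Assumed q | MUS only (70.8 x q) | MUS+BPTx (47.2 x q) | Artificial arm difference (10 points x q) |
|---|---|---|---|
| 5% | 3.5 | 2.4 | 0.5 points |
| 10% | 7.1 | 4.7 | 1.0 points |
| 25% | 17.7 | 11.8 | 2.5 points |
| 50% | 35.4 | 23.6 | 5.0 points |

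SAP 13 reports that relatively few participants met the failure criteria, so the planning rates probably overstate the exposure.

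**The case against.** The strongest reply is that the rule is ordinary data cleaning. An additional treatment entered by mistake as an AE goes to the form made for it, and the wording is qualified at both ends. The detailed AE capture sits in a manual of procedures that is not among the documents. Moved events are also not lost: SAP 9.2 categorises retreatment by type, SAP 3.1.3 plans to compare proportions and types between arms, and SAP 7.4 sends sling revision rates by arm to the DSMB. Safety p-values are descriptive only (SAP 7.7), and efficacy results are untouched.

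Much of this stands. It does not settle the reoperation row. SAP 10.2 itself defines a return to the operating room for recurrent symptoms as an adverse event, so such an entry is no logging error. The qualifiers give no criterion for which entries stay. A revision for retention or persistent SUI that is reported only as retreatment is shown as an efficacy outcome and not as a harm.

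A reader might infer more than the documents support:

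- *That the whole complication table is depleted.* Symptom rows assessed from questionnaire responses do not change when an AE entry is moved.
- *That serious events are removed.* Neither 10.3 nor 16.1 says so, and Protocol 7.4 has investigators report them separately to the IRB and the data coordinating center. The SAP merely fails to exempt them.
- *That 71 and 47 women lose an AE record.* Those are counts of any additional treatment, including medication and behavioral therapy, which need not involve an AE.
- *That visits for infection, pain or retention are swept up too.* CRF #31 codes 1, 6, 7 and 9 are not failure codes, so they do not trigger the rule.

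**Conclusion.** SAP 16.1 and 10.2 conflict for events that are both a treatment failure and a postoperative complication, and the SAP states no reconciliation. The problem is confined mainly to the reoperation row, the rows linked to it, and the general AE summaries.

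The proper wording is that these displays may be undercounted. Nothing in the documents shows that a record was in fact lost. The absolute numbers are small, about 0 to 2.4 revisions per arm if the cited 0-1% applies, but with so few events the loss of one or two could largely empty the row. A difference between arms is plausible and cannot be sized, because the share of failures with an AE entry is unknown.

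This is a should-fix point. It leaves the primary and secondary efficacy analyses as they are.

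**What to change.** 1. **SAP 16.1.** Replace the removal rule: an AE that is also a treatment failure stays on the AE log and is additionally recorded on CRF #31. State that SAEs are never removed from the log.
2. **SAP 10.2.** Name CRF #31 codes 12, 13 and 17 as a source for the reoperation row and the linked readmission and emergency visit rows, de-duplicated against the AE log by participant and date.
3. **Data check.** Query whether any AEs were removed under the rule, and restore those that were before the safety tables are final.

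The cost is SAP wording, one data query, and a merge of two existing forms. No new data are needed.

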16.2 Missing Data and Multiple Imputation

Sensitivity analysis to see the impact of missing data on the primary outcome (UDI Total score) and the dryness and MID indicators will be performed using multiple imputation. Missing data at 3, 6, and 12 months will be imputed using non-missing data from prior time points (including baseline) to inform the imputed values as well as age, treatment, race, ethnicity, BMI, smoking status, estrogen use (oral/patch), site, incontinence episode group (from randomization), vaginal delivery count, and private insurance indicator. Missingness will first be assured to monotone missing (i.e. ensure not missing prior time points when later time points are present) 25 times using MCMC methods, then all other missing data will be imputed for each of the 25 monotone-missing datasets using regression and logistic imputation methods. Each imputed dataset will be fit using the models described in Section 9.3. Differences between groups for each imputed dataset will then be combined to estimate average effects and standard errors and compared to the model without imputation. All imputation will be performed using SAS v9.4.

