7.3 Handling of Dropouts and Missing Data

Missing data mechanisms will be explored, and sensitivity analyses will be conducted on primary outcomes to assess the robustness of the described analyses. Methods employed for sensitivity analyses may include multiple imputation or inverse probability weighting methodology. Imputation is not planned for secondary analyses. For further details on sensitivity analyses involving missing data see Attachment 16.2.

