clinical site will be included as random intercepts to account for correlation between outcomes of patients treated by the same clinical site. Consistent with the description of the primary analysis in the protocol, analyses of primary and secondary outcomes will also include independent variables for time and request for additional treatment. If differences between treatment groups are to be assessed at multiple time points (for example, 6 and 12 months), then longitudinal modeling will be used and the interaction between time and treatment groups will be included. Unless otherwise noted, all analyses of continuous efficacy variables (e.g., QOL scales) will be performed using general linear mixed models. Variables with distributions substantially different from normal will be transformed prior to analysis. Models will be adjusted for clinical site and UUI severity group. If there are not enough patients per clinical site to include the variables in the models as fixed effects, clinical site will be included as a random intercept to account for correlation between outcomes of patients treated by the same clinical site. If differences between treatment groups are to be assessed at multiple time points (for example, 6 and 12 months), then longitudinal modeling will be used and the interaction between time and treatment groups will be included. Under the assumption that any missing outcome data will be missing at random (thus, missing UDI scores at 12 months may be related to both 3 and 6-month outcomes and covariates), this model will produce more accurate estimates in the presence of missing data than one that models only outcomes at 12 months. For the primary outcome and for secondary outcomes, models will include 2- and 3-way interactions between treatment assignments, time, and request for additional treatment.

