9.3 Primary Analysis Methods

The mean change from baseline in UDI scores will be compared between groups at 1 year. As explained previously, participants will be permitted to seek additional treatment for SUI and/or OAB after 3 months following MUS. Because such treatment is expected to impact the participant's UDI score at 1 year, we will use an analysis method that accounts for the impact of additional treatment. Specifically, a general linear mixed model will be constructed to model change from baseline in UDI scores using scores recorded at time points up to 1 year following MUS. For participants who request additional treatment, only UDI measurements up to the time of additional treatment will be included in the model, and measurements taken between additional treatment and 1 year will be considered missing for the purpose of the primary analysis. The model will include fixed effects for treatment group, time, request for additional treatment, and interactions between those variables. It will also be adjusted for the design effects of stratification by center and by baseline urge IE group. Thus, the models will allow for different trajectories of change for women who are or are not randomized to BPTx and for those who do or do not request additional treatment. A statistical test based on the model will be conducted to assess whether mean changes from baseline in UDI scores at 1 year are significantly different between the two treatment groups, accounting for the percent of women in each group who request additional treatment. Sensitivity analysis will be conducted to test the robustness of test results to model specifications.

We will report whether change in total UDI score between baseline and one year is significantly different in the two groups. If the difference is statistically significant, the potential clinical significance of the difference will be discussed. We recognize that our sample size would allow us to find a difference between groups that is statistically significant yet smaller than published MIDs for total UDI score for women with MUI. However, published MIDs were calculated based on populations that may be somewhat different from the one targeted for enrollment in ESTEEM, and a secondary aim of ESTEEM is to explore whether the true MID in this population differs from previously published values.

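### SAP 16.2 imputes UDI-total without request for additional treatment, leaves the handling of scores after additional treatment open, and no specified check departs from missing at random

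*SAP*

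**What the plan says.** SAP 16.2 describes the imputation: "Missing data at 3, 6, and 12 months will be imputed using non-missing data from prior time points (including baseline"), together with "age, treatment, race, ethnicity, BMI, smoking status, estrogen use (oral/patch), site, incontinence episode group (from randomization), vaginal delivery count, and private insurance indicator". Missingness is first made monotone, 25 times, and regression methods fill the rest. Then "Each imputed dataset will be fit using the models described in Section 9.3".

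On that model, SAP 9.3 says: "The model will include fixed effects for treatment group, time, request for additional treatment, and interactions between those variables". SAP 9.1 adds that, for primary and secondary outcomes, "models will include 2- and 3-way interactions between treatment assignments, time, and request for additional treatment". Section 9.3 also restricts the data: "For participants who request additional treatment, only UDI measurements up to the time of additional treatment will be included in the model". It treats later scores as missing, and ties that to the primary analysis.

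On assumptions, SAP 9.1 reads "Under the assumption that any missing outcome data will be missing at random". SAP 7.3 reads "Methods employed for sensitivity analyses may include multiple imputation or inverse probability weighting methodology" and refers to 16.2 for detail. The rule in SAP 9.5.1 that gives requesters the worse outcome covers dichotomous voiding-frequency outcomes, not the UDI.

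Protocol 3.4.1.c and 5.5.2 ask women to complete the outcome measures when they start additional treatment. SAP 16.2 names only the 3-, 6- and 12-month visits and baseline, and does not say whether this extra UDI counts as a prior time point.

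**The concern.** An imputation model should contain the terms that the analysis model estimates. Here request is missing from the first and interacts with arm and time in the second. Once scores after additional treatment are blanked, hardly any requester has a usable 12-month score. If imputed values are kept, they fill the requester-at-12-months cells, and they are drawn as if these women were non-requesters with the same score history.

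Whether they are kept is not stated. Three readings are open:

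- **Impute and keep:** later scores are blanked, imputed and retained.
- **Exclude at the fit:** the 9.3 restriction applies again, so requesters' imputed later scores never enter.
- **Restore:** observed scores after additional treatment return, because 9.3 blanks them for the primary analysis only.

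Two analysts could therefore run different checks. Under none of them would agreement with the primary model show that the result survives if requesters or dropouts fare worse than their recorded scores predict.

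**Working it through.** **Inputs from the documents.** Request rates of 30% (MUS) and 20% (MUS+BPTx), SAP 6. SD 50.4 for UDI-total, SAP 6.1. From SAP 6.3: 200 per group, 15% dropout, 472 in total, and detectable differences of 19 points (90% power) and 16.5 points (80%).

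**Assumptions, because the documents give no values.** Between-visit correlation r of 0.4, 0.6 or 0.8. A requester deficit of 35 points at month 12 (range 20 to 50), equal in both arms.

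**1. The plan's own figures.** 200/0.85 = 235.3, so 236 per arm and 472 in total, as stated. If requesters contribute nothing at month 12, 140 and 160 women contribute, and SE = 50.4 × √(1/140 + 1/160) = 5.83. Power is then 90.3% for 19 points and 80.8% for 16.5, which matches the SAP. Working back from the stated differences, 16.5/(1.960 + 0.842) = 5.89 and 19/(1.960 + 1.282) = 5.86. I use about 5.9.

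**2. How much is missing.** Requesters: 0.30 × 236 = 70.8 and 0.20 × 236 = 47.2, or 118 of 472 (25%). With independent 15% dropout, 236 × (1 − 0.70 × 0.85) = 95.6 and 236 × (1 − 0.80 × 0.85) = 75.5. About 171 of 472 (36%) would lack a usable 12-month score.

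**3. Impute and keep.** Shift of the arm contrast toward the null = (0.30 − 0.20) × deficit × share of the deficit lost. For a 35-point deficit:

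| Case | Share lost at r = 0.4 / 0.6 / 0.8 | Shift, points |
|---|---|---|
| Request depends only on a recorded score (simulated) | 0.6% / 0.2% / −0.5% | 0.02 or less |
| Constant deficit, one prior follow-up score: 1 − r | 60 / 40 / 20% | 2.1 / 1.4 / 0.7 |
| Constant deficit, two prior scores: (1 − r)/(1 + r) | 43 / 25 / 11% | 1.5 / 0.9 / 0.4 |
| Late deficit (0, half, full at months 3, 6, 12), two prior scores: 1 − 0.5r/(1 + r) | 86 / 81 / 78% | 3.0 / 2.8 / 2.7 |
| Late deficit, month-3 score only | 100% | 3.5 |

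Simulation with 400,000 women per arm agreed with the formulas to within 0.01 in the share lost. In SE units, the constant-deficit range is 0.4/5.9 = 0.07 to 2.1/5.9 = 0.36, and the ceiling is 3.5/5.9 = 0.6. A simulation at trial size (236 per arm, r = 0.6, half the requests after month 3 and half after month 6, 15% dropout) gave 0.6, 1.1 and 1.5 points for deficits of 20, 35 and 50, with simulation SE 0.12. At assumed request rates of 15% and 10%, the constant-deficit range falls to 0.2 to 1.1 points.

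**4. Exclude at the fit.** Requesters' imputed later scores do not enter, so nothing is attenuated. The check then covers ordinary missed visits only.

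**5. Restore.** If additional treatment removes a gap of 20, 35 or 50 points, the contrast moves by 0.10 × gap = 2.0, 3.5 or 5.0 points (simulated: 2.0, 3.5, 5.2).

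**6. What a shift run would show.** Higher UDI is worse. The significance limit is about 1.96 × 5.88 = 11.5 points. Holding the SE fixed, for an observed 16.5-point benefit the shift in the BPTx arm alone that removes significance is (16.5 − 11.5)/0.20 = 25 points in requesters (50 if 10% request), or 5.0/0.15 = 33 in dropouts. For a 19-point benefit the figures are about 37 (75) and 50. A +35 shift in both arms' requesters moves the contrast 0.10 × 35 = 3.5 points in favour of BPTx. In BPTx requesters alone it moves 0.20 × 35 = 7.0 points against BPTx.

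**The case against.** **The literal reading is exclude at the fit.** SAP 16.2 fits the 9.3 model, and 9.3 describes which measurements enter that model. On that reading the omission attenuates nothing. This largely stands, and I treat it as arguably the more literal reading. But 9.3 ties the blanking to the primary analysis, 16.2 does not repeat it, and on this reading the check says nothing about requesters after additional treatment.

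**The primary model already separates requesters.** Its interactions give them their own trajectory, much like a pattern-mixture model, so comparing it with an imputation that ignores request contrasts two assumptions. This stands in part, under impute-and-keep only. The primary model has few or no requester scores at month 12 to learn from, the contrast does not extend to dropouts, and neither analysis sets a level of deterioration.

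**Adding request would not repair month 12.** This stands. With later scores blanked, no woman who started additional treatment before month 12 has a valid 12-month score; in the trial-size simulation there were none. A covariate alone is therefore not enough.

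**A missing-not-at-random check is not excluded.** SAP 7.3 promises to explore missing-data mechanisms, and its list of methods is permissive. This stands: the SAP does not bar such an analysis, but it specifies none.

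**Few women failed.** SAP 13 describes the number meeting the failure criteria as relatively small, so the effects may be below the 30% and 20% illustration.

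**Conclusion.** The point holds as a modest gap in a sensitivity analysis. The imputation model lacks a term of its own analysis model, the handling of scores after additional treatment is unsettled, and no specified check of UDI-total leaves missing at random.

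A reader might infer that the omission biases the primary result or could produce a false superiority claim. The documents do not support that. The primary test does not use 16.2. Under impute-and-keep, with equal deficits and more requests in the control arm, the contrast moves toward the null: 0.4 to 2.1 points for a constant 35-point deficit, at most 3.5 if the deficit emerges late, and nothing if request depends only on recorded scores. Restored scores could matter more, at about 2 to 5 points, but only if additional treatment removes the assumed gap.

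These sizes rest on assumed correlations, deficits and timing. The undefined handling rule and the absent missing-not-at-random check do not depend on them.

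**What to change.** In SAP 16.2:

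1. State which handling applies to scores after additional treatment, consistent with 9.3, and do not restore observed scores after additional treatment in this check.
2. Add request, and its interaction with arm, to the imputation model at the visits where it can be estimated. Use the UDI collected just before additional treatment as an added input, without overwriting an observed scheduled score. For a woman with only a month-3 score and a constant deficit, this second score cuts the share lost from 60/40/20% to 43/25/11%.
3. Because request is barely identified at month 12, add a shift (tipping-point) run on the imputed 12-month scores of requesters, and separately of dropouts. Run it in both arms and in the BPTx arm alone, for example at 0, +10, +20, +35 and +50 points, and report the shift at which the conclusion changes. This run must keep the imputed scores in the fit, whatever rule is chosen under (1). If controls request more often, only the BPTx-arm run among the requester shifts can challenge a positive result.

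The cost is some SAP wording and a few extra runs in the same software, on data the protocol already asks for. The shift values are a judgement. SAP 13 reports in the past tense that a survival method was replaced; if outcomes have already been unmasked, the shift runs should be labelled post hoc.
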